## 17. DATA ANALYSIS PLAN

Aim 1: To assess the efficacy of CBT-L's impact on loneliness, negative affect and the quality and quantity of social interactions among individuals with OUDs. Outcomes variables will include loneliness, negative affect, and the quality and quantity of social interactions. We will conduct mixed regression modeling with condition, time, time by condition interactions, and relevant covariates included as predictors.

Aim 2: To assess the cognitive, affective, and behavioral mechanisms of the effect of CBT-L on opioid use trajectories. Outcome variables for this aim will include opioid use and craving. Exploratory mediation analysis will be conducted to examine whether CBT-L reduces opioid use trajectories and whether these reductions occur due to reductions in loneliness and/or negative affect and social interaction quality/quantity.

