# The association between loneliness and substance use Principal Investigator – [name]

## 1. PURPOSE OF STUDY

The proposed study will be the first to assess these cognitive, affective, and behavioral pathways by which loneliness impacts opioid use. Individuals with an opioid use disorder (OUD) reporting loneliness (N = 125) will be randomized to either a 6-session Cognitive-Behavioral Therapy for loneliness (CBT-L; n = 63) or a 6-session education control condition (n = 62), both delivered via telehealth. Telehealth delivery can be easily implemented and can increase reach and access to individuals not engaged in treatment. We will use an established brief CBT manual to address loneliness. We will assess loneliness, negative affect (i.e., depression and anxiety), and the quality and quantity of social interactions prior to, during, and after the intervention to evaluate the subsequent impact on opioid use trajectories. Participant will complete questionnaires pre-treatment, post-treatment, and at 1- and 2-months post-treatment. Given the need to elucidate mechanisms of opioid use and to test novel treatment approaches to reducing opioid use, we propose the following specific aims in this pilot study:

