# Aim 2: To assess the cognitive, affective, and behavioral mechanisms of the impact of CBT-L on opioid use trajectories

Hypothesis: CBT-L will reduce opioid use relative to the education control and these reductions will occur due to reduced loneliness, negative affect, and increased quality and quantity of social interactions.

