Substance use is among the several unhealthy behaviors through which loneliness relates to increased premature mortality. Loneliness has been linked to tobacco and alcohol use in numerous studies,  including a national 10-year longitudinal study of over 3,000 people, where greater loneliness was associated with a 70% decreased likelihood of smoking cessation.  In cross-sectional data with 18-39 year olds, loneliness was associated with problematic drinking after accounting for depression, alcohol consumption, and coping style. 

Bohnert and Ilgen postulate that large-scale social factors (e.g., lack of employment opportunities, socioeconomic inequities) increase opioid use leading to depression and social isolation. The opioid epidemic further impacts communities through harmful effects on social networks and social cohesion emphasizing a need to increase meaningful social interactions. Opioid use can be reinforced through coping with social isolation that occurred as a result of finding social contact less rewarding and being concerned with the stigma attached to opioid use. Indeed, loneliness increases opioid use, is associated with a variety of negative consequences among individuals using opioids and is a critical factor that needs to be addressed in response to the opioid epidemic

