# 5. SUBJECT POPULATION

We will nationally recruit 125 adults with OUD for this randomized clinical trial. We estimate that our screen failure rate will be approximately 10-30%. We estimate attrition from the consent and baseline assessment to the end of the 2-month follow-up to be approximately 20%.

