## 9. STUDY PROCEDURES

Screening: The project coordinator will screen by phone following a script. Potential participants will provide verbal consent to complete the screening measures. Those individuals meeting eligibility who are interested in participating will be scheduled for a telehealth-based appointment to go over Consent, complete eConsent, and conduct a baseline assessment. Assessments and Intervention: Participants will be enrolled following consent and will complete the baseline assessment. Following the baseline assessment, participants will be randomized to condition (control or experimental) by a computer-generated algorithm. Participants will schedule a convenient time for their telehealth-based intervention sessions. Mid-treatment, posttreatment, and 30- and 60-day post-treatment follow-up assessments will also be conducted by telehealth. Participants will be paid \$40 each for the baseline and post-treatment assessment, \$20 for the mid-treatment assessment and \$30 each for the 30-day and 60-day follow-up assessments. Participants will also be paid \$20 for completing the first 3 sessions within 4 weeks. The posttreatment assessment will also include an exit interview for participants to describe acceptability of the intervention. All assessments and interventions will be conducted via Zoom (including toll-free phone option) or phone. If requested, participants will be sent a letter indicating study activities completed.

Randomization: We will randomize at the participant level using block randomization in groups of 4. All demographic and outcome variables will be assessed for baseline equivalency. Any between-group baseline differences will be controlled for statistically in all subsequent analyses with baseline differences being defined here as any absolute standardized mean difference (Cohen's d) greater than or equal to .15.

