#### Measures

When feasible, well-validated measures available as common data elements will be used. All data collection will be completed by telehealth.

Loneliness: The 20-item Revised UCLA Loneliness Scale will be our primary outcome measure. We will use the 5-item NIH Toolbox Loneliness Scale  as our loneliness screening measure. The NIH Toolbox Loneliness Scale is correlated highly (r = .80) with the Revised UCLA Loneliness Scale.  T-scores >60 indicate loneliness scores 1 standard deviation above the mean and will be used to assess eligibility. 

Opioid-related outcomes. Opioid Use Disorder: The OUD module in the SCID-5-RV will be used to identify an OUD at screening and will be re-assessed at the final follow-up. Opioid use: We will use the Timeline Follow Back (TLFB) from the 60 days prior to baseline through to the end of participation in the study (i.e., 60-day follow-up) to assess days used opioids and percent days abstinent. The TLFB will be completed at each assessment time point so there are shorter intervals facilitating participant recall of their substance use. The TLFB has long-

Page 7 of 20

standing strong psychometric properties and is highly correlated with urine drug screen results, which would be difficult to obtain because there is no in-person contact in the current study. Another advantage of TLFB is that participants may be more honest about their opioid use because there will be no in-person meetings thus increasing relative anonymity and decreasing social desirability/ under-reporting. *Craving: The Penn Craving Scale* (PCS) is a 5-item measure assessing aspects of past-week craving for opioids. Research supports the psychometric properties of the opioid version of the scale. *Consequences of substance use*: The Inventory of Drug

Use Consequences (InDUC-2) will be used to assess drug use consequences in the following domains:

impulse control, social responsibility, physical, intrapersonal and interpersonal. Consequences will be assessed for the last 3 months at baseline and the follow-up will be since the previous assessment.

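### Opioid use, the only secondary outcome, has no between-arm model of its own, and its baseline value is adjusted for only when the arms differ by |d| ≥ .15

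*Combined protocol and SAP*

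**What the plan says.** The Aim 2 hypothesis is directional and compares the arms: "CBT-L will reduce opioid use relative to the education control and these reductions will occur due to reduced loneliness". Table 1 (section 9, Measures) puts TLFB opioid use alone under the secondary-outcome heading.

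Section 17 lists outcomes aim by aim. Under Aim 1 it names a mixed regression with condition, time and their interaction, for loneliness, negative affect and social interactions. Under Aim 2 the outcomes are opioid use and craving, and the only analysis named is: "Exploratory mediation analysis will be conducted to examine whether CBT-L reduces opioid use trajectories". The same sentence goes on to ask whether such reductions come about through loneliness, negative affect or social interaction.

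Three other places bear on this.

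- **Baseline handling** (section 9, Randomization): "Any between-group baseline differences will be controlled for statistically in all subsequent analyses", where a difference means an absolute standardised mean difference of .15 or more.
- **Metric and windows** (section 9, Measures): the TLFB runs from 60 days before baseline to the 60-day follow-up, "to assess days used opioids and percent days abstinent". On timing: "The TLFB will be completed at each assessment time point so there are shorter intervals". No choice is made between the two metrics.
- **Intended order** (section 1): the mediators are measured "to evaluate the subsequent impact on opioid use trajectories".

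**The concern.** The trial has a ranked outcome with a directional hypothesis, and the estimate that answers it is left inside an exploratory mediation. A mediation can yield a total arm effect, but section 17 gives no model, metric or baseline handling for one. The analyst would choose these after seeing the data.

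The baseline rule is a stated choice rather than a gap. It makes adjustment depend on the imbalance that happens to arise, although the value of a baseline covariate lies mainly in how well it predicts the outcome. Where past use predicts later use, leaving it out discards precision.

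A smaller matter is timing. The TLFB at a visit looks back over the preceding interval, while loneliness, affect and social interaction are scored at that visit. Section 17 does not say which visit supplies the mediator and which window supplies the outcome. Pairing them at the same visit would put the reported use before the mediator. Section 2 cites a view in which social factors "increase opioid use leading to depression and social isolation", so use may also drive a mediator. The data are meant to guide a larger trial (section 12), so a misread mechanism would carry forward.

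**Working it through.** The plan gives no alpha, power, effect size or SD, so there is no figure of its own to reproduce.

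**Inputs from the documents.** N = 125, split 63 and 62 (sections 1 and 4). Attrition from consent and baseline "to the end of the 2-month follow-up to be approximately 20" per cent (section 5), so 125 × 0.8 = 100, or 50 per arm. Adjustment threshold .15 (section 9).

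**Assumptions.** Two-sided alpha .05, an effect of .5 SD on use, a baseline-to-outcome correlation r of .4 to .7, and normally distributed outcomes.

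**Step 1: how often the rule triggers by chance.** P = 2 × [1 − Φ(.15/SE)], with SE = √(1/n₁ + 1/n₂).

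- 63 v 62: SE = .179, ratio .84, P = .402.
- 50 v 50: SE = .200, ratio .75, P = .45.

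Baseline use would go unadjusted in roughly 55–60% of randomisations.

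**Step 2: power at 50 per arm.** With baseline always included, power ≈ Φ(.5/(.2 × √(1 − r²)) − 1.96).

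- r = .4: Φ(2.73 − 1.96) = .78.
- r = .7: Φ(3.50 − 1.96) = .94.

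Without adjustment it is Φ(2.50 − 1.96) = .71. The section 9 rule mixes the two, so it was simulated (6,000 trials per setting, using t tests, which give slightly lower values than the formula):

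| r | Section 9 rule | Always adjusted |
|---|---|---|
| .4 | .730 | .763 |
| .5 | .749 | .806 |
| .6 | .790 | .870 |
| .7 | .828 | .932 |

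**Step 3: type I error.** At zero effect the rule gives .033–.044, against .048–.054 when always adjusted. When baseline is left out, the arms are already known to be close on it, so the estimate varies less than its standard error says. The test is therefore conservative.

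**Step 4: change from baseline as an alternative.** Power ≈ Φ(.5/(.2 × √(2(1 − r))) − 1.96).

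- r = .4: Φ(2.28 − 1.96) = .63.
- r = .7: Φ(3.23 − 1.96) = .90.

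Simulation gave 62–89%, which is below always adjusting throughout.

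**Step 5: the mediation ordering.** These figures illustrate a mechanism, because every coefficient is assumed: n = 100, 2,000 trials per setting, autocorrelation .6 for use and .5 for loneliness, no effect of loneliness on use, both paths required to be significant.

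- **CBT-L acts only on use** (.3–.8 SD), with use raising loneliness by .2–.4: false mediation is 3–52% for same-visit pairing and 0–2% for a lagged analysis that also adjusts for use before the mediator. Always adjusting same-visit pairing for baseline does not help (3–55%).
- **Price of that extra adjustment.** If loneliness acts on use within a window (path .2 or .3), power falls from 45% or 65% to 16% or 27%. If it acts only on later windows, power barely moves (52% to 51%, 69% to 68%).

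**The case against.** The strongest reply on the arm effect is that section 17 speaks of trajectories. A trajectory model would normally take baseline as its first point, whatever section 9 says, so the loss in Step 2 would belong to an analysis the plan does not describe. This stands in part. The figures in Step 2 apply to an analysis of post-baseline use, and section 17 does not say which kind is meant. But using baseline as a starting point to be subtracted also falls short of always adjusting (Step 4), so the recommendation survives either reading.

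Two stronger readings are tempting. A reader might infer that the planned mediation would report a false mechanism in a large share of trials. If CBT-L changes loneliness but not use, and the reverse path is .1–.4, same-visit pairing does give 19–67%. The documents do not support that as a headline. Section 17 asks what explains reductions in use, and in this case there are none. Requiring a significant reduction as well brings the same-visit rate to 0.4–2.6%. Section 17 sets no such formal gate, but it is the natural reading. A reader might also infer that same-visit pairing is planned. It is not stated, and section 1 points the other way.

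Other points stand. The cited reverse path concerns depression and social isolation, and section 2 separates social isolation from loneliness. No recall period is given for the mediator scales, so how far reported use precedes them is uncertain. The mediation is labelled exploratory, in a study that section 1 calls a pilot.

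**Conclusion.** The concern holds for the between-arm effect on opioid use. The only secondary outcome has a directional hypothesis and no model of its own, and it cannot be assumed that the Aim 1 model carries over. The stated baseline rule costs about 3 to 10 percentage points of power (.763 − .730 and .932 − .828) and pulls type I error down to about 3–4%. Those sizes rest on 50 per arm, a .5 SD effect and correlations of .4–.7, none of which is in the plan except the sample size after attrition. The rule does not inflate false positives; what it loses is efficiency.

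The mediation part is a brief addition. The plan leaves the ordering open but does not choose a wrong one. The risk is real mainly if CBT-L lowers use by a route other than loneliness, and at the low end of that case it is below 5%. The change is worth making before analysis, but it does not threaten the trial's primary question.

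**What to change.** 1. Add to section 17, under Aim 2, a between-arm mixed model for opioid use, separate from the mediation. The outcome is percent days abstinent in each TLFB window, which also removes the problem of unequal window lengths. The predictors are condition, time and condition-by-time, with the 60-day baseline value always a covariate, whatever the baseline d. With baseline as a covariate, the arm effect is the condition difference at the post-baseline windows, or averaged over them. The interaction alone does not give it. The sponsor should name in advance which of these is the secondary-outcome estimate.
2. In the exploratory mediation, let the post-treatment mediator predict use only in the 30- and 60-day follow-up windows, adjusted for arm, baseline mediator and baseline use. Make this the lead version.
3. Add a sensitivity version that also adjusts for use in the window before the mediator. State that it guards against reverse causation but can lose much power if mediation acts within a window, and that neither version removes unmeasured confounding.

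The cost is one fixed covariate and SAP wording. All the data are already scheduled.
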